## Protocol Revisions

No.	Version No.	Date	Description of Changes
1	1.0	19 January 2022	N/A
2	1.1 CA	23 MAY 2023	
This version is a Canadian specific version.
 

• Addition of ISO 14155 compliant sections

• Changes to sample size calculation and statistical methods

• Refinement of eligibility criteria

• Changes to some secondary endpoints

• Addition of normal tissue and margin tissue

• Removal of neurosurgeon assessment of images

• Change of Canadian Primary Investigator and CRO

3	1.2	July 11, 2023	Number of specimens and basis for calculation, modification of secondary endpoints changed
4	1.3	March 6, 2024	

• Correction to study summary: objective and secondary endpoints.

• Updated the informed consent section (6.4) to indicate that patients will first be approached for the study by a clinical staff member not part of the research study, and that ICF will be obtained by a study team member not part of the circle of care.

• Overall improved consistency of term and symbol use.

## Synopsis

Protocol Title	A prospective, multi-centered, assessor-blinded clinical performance study to evaluate the sensitivity and specificity of the proposed cell/tissue histopathology image processor cCeLL – Ex vivo (Confocal Fluorescence Endomicroscopy) for intraoperative brain tumor diagnosis.
Sponsor	VPIX Medical Inc.
Sites	Korea University Anam Hospital, Seoul, S. Korea Seoul National University Hospital, Seoul, S. Korea Samsung Medical Center, Seoul, S. Korea, Unity Health- St. Michael's Hospital, Toronto, ON, Canada
Coordinating Investigator	[name] MD M.M.Sc Ph.D Korea University College of Medicine
Study Objective	The purpose of this clinical study is to confirm sensitivity and specificity of the cCeLL – Ex vivo in intraoperative brain tumor diagnosis as compared to analysis with frozen section. 

○ The existing workflow for intraoperative brain tumor diagnosis involves tissue biopsy, processing, analysis and confirmation by a pathologist using a frozen section, and relaying the result back to the surgeon.

○ The current intraoperative diagnosis based on frozen section analysis is time-, resource-, and labor-intensive. The process takes over 40 minutes on average, but may take longer if biopsied specimen is insufficient or requires repeated analysis. Thereby the development of an efficient device that allows intraoperative real-time diagnosis is enforced.

○ The “Digital Biopsy” imaging method, using micro-sized confocal laser endomicroscopy, is an emerging technology that enables intraoperative visualization of real-time high-resolution brain tumor tissue images.

○ Neoplastic brain tissue biopsied from participant will be visualized and images will be captured using cCeLL – Ex vivo. The corresponding biopsy samples will be examined with standard frozen-section analysis (H&E slide), to evaluate the sensitivity and specificity of cCeLL – Ex vivo in the diagnosis of brain tumors. This study will also be able to verify the potential of Confocal Endomicroscopy to replace the current standard frozen-section analysis, in intraoperative brain tumor diagnosis.

Background	Prospective, multi-centered, assessor-blinded, clinical performance study
Study Design	
Sample Size	
The sample size refers to the number of analyzable tissue samples collected from participants. There may be multiple samples collected from each participant. As it is expected that the 30% of tissue samples will be non-analyzable, the collection of tissue samples will be larger than the target sample size.
 
The total samples to be collected will be up to 358 samples (286 cancer samples, 72 normal samples)
 

- Korea University Anam Hospital: 51 samples (cancer: 42 samples, normal: 9 samples)

	

- Seoul National University Hospital: 82 samples (cancer: 72 samples, normal: 10 samples)

- Samsung Medical Center: 82 samples (cancer: 72 samples, normal: 10 samples)

- St.Michael's Hospital, Unity Health: 143 samples collected from a total of 65 participants (cancer: 100 samples, normal: 43 samples)

 
After excluding the non-analyzable tissue samples, we expect to conclude the study with a total of 250 samples (200 samples for cancer, 50 samples for normal)
 

-Korea University Anam Hospital: 36 samples (cancer: 30 samples, normal: 6 samples)

-Seoul National University Hospital: 57 samples (cancer: 50 samples, normal: 7 samples)

-Samsung Medical Center: 57 samples (cancer: 50 samples, normal: 7 samples)

-St.Michael's Hospital, Unity Health: 100 samples collected from a total of 50 participants (cancer: 70 samples, normal: 30 samples)

																			
Basis for Calculating the Number of Acquired Images	
The data for agreement, sensitivity and specificity can be summarized as in the table below. For agreement, the terms agree and disagree are with respect to each other. For sensitivity and specificity, the terms agree and disagree are with respect to truth. So for sensitivity, truth is tumor and for specificity truth is not tumor.
 
Agreement Table
 

	cC	

FS Results	Agree	DisAgree		

Agree	b	a+b	

Disagree	c	d	c+d	

	a+c	b+d	nT	

 
The estimate of agreement is <math>p_{AG} = (a+d)/n_T</math>. It is desired to test the hypothesis that the agreement is greater than 80%. This is compatible with the expected result that both the sensitivity and the specificity will be about 90%. Thus the hypothesis to be tested is:
 $H_0: \pi_{AG} = 80\% \text{ vs } H_A: \pi_{AG} > 80\%$ 
Where <math>\pi_{AG}</math> is the percent agreement between Frozen Section and cCeLL. This will be tested utilizing the exact binomial test. Estimates of agreement from the pilot study indicate that the agreement will be greater than 86%. In this study, there will be 250 subjects available for analysis for the estimation and testing of agreement. For outcome results, if the agreement is 86%, with the sample size of 250, the probability the estimated agreement will be greater than 80% is greater than 90%.
			cC		FS Results	Agree	DisAgree		Agree	b	a+b	Disagree	c	d	c+d		a+c	b+d	n T
		cC																		
FS Results	Agree	DisAgree																		
	Agree	b	a+b																	
Disagree	c	d	c+d																	
	a+c	b+d	n T																	

	
Sensitivity Table – This is only tabulated when the truth standard is positive for tumor.
 
Agreement Table with Tumor Truth
 
  
 	cC		
 
 FS Results	Agree w/Truth	DisAgree w/Truth		
   
 Agree	e	F	e+f	
 
 Disagree	g	H	g+h	
 
 	e+g	f+h	n1	
  
 
The sensitivity of the Frozen Section is given by <math>p_{SenF} = (e+f)/n_1</math> and the sensitivity of cCeLL is given by <math>p_{SenC} = (e+g)/n_1</math>. It is desired to demonstrate that the sensitivity of cCeLL is non inferior to that of Frozen section.
 
The non inferiority of the sensitivity of cCeLL result versus the sensitivity of the Frozen Section is given as:
 $H_0: \pi_{SenF} - \pi_{SenC} > \Delta \text{ versus } H_A: \pi_{SenF} - \pi_{SenC} \leq \Delta$ 
Here <math>\pi_{SenF}</math> is the true sensitivity for Frozen Section and <math>\pi_{SenC}</math> is the true sensitivity for cCell. Where <math>\Delta</math> is the non inferiority limit. In this study, it is proposed to utilize a <math>\Delta=0.05</math> (5%). If that <math>\Delta</math> is used and the anticipated sensitivity is 90%, then with a sample size of 200 tumor positive samples the probability the difference between the estimated sensitivities is greater than 5% is greater than 90%.
			cC		FS Results	Agree w/Truth	DisAgree w/Truth		Agree	e	F	e+f	Disagree	g	H	g+h		e+g	f+h	n 1
		cC																			
FS Results	Agree w/Truth	DisAgree w/Truth																			
Agree	e	F	e+f																		
Disagree	g	H	g+h																		
	e+g	f+h	n 1																		
Eligibility Criteria	
Inclusion Criteria
 
The biological specimens (hereafter referred to as ‘Tissue’) and/or images to be used in this trial must be collected from patients who satisfy all of the following inclusion criteria
 
 
1. Male or female patients <math>\geq 19</math> years of age;
 
2. Patient is suspected to have a brain tumor and has been scheduled for neurosurgery with a potential tumor resection;
 
3. Patient is willing and able to provide informed consent and understand its content.
 
 
Exclusion Criteria
 
Tissue and/or images to be used in this trial must be collected from patients who do not meet any of the following exclusion criteria:
 
 
1. Patients has undergone several surgeries on the lesion of interest.
 
																				
Study Device	cCeLL - Ex vivo (Clearance No. 21-311)																				
Study Duration	18 months from the start date of the study																				
Study Procedure	1) Samples will be collected from consented participants who have satisfied the eligibility criteria.																				

	
2) Tissue will be removed as part of the standard neurosurgical procedure. Normal tissue obtained from inevitable resection during the course of surgery. There will be no deviation from normal surgical practice to acquire tissue samples.
 
3) Image recordings of sample tissue using cCeLL – Ex vivo are taken and the obtained data is stored (CC).
 
4) cCeLL – Ex vivo image data of the collected samples is sent to the central core.
 
5) The result of frozen section analysis (FS) will be collected from the pathology department of each site.
 
6) The result of permanent section analysis (PS) of corresponding paraffin-embedded tissue section (PS) will be collected from the pathology department of each site. PS will serve as a reference standard to the analysis result of CC and FS.
 
7) An interpreting pathologist will analyze given images (CC-H) and is not allowed to review the reference standards (PS) until all interpretations have been completed.
 
8) The cCeLL – Ex vivo image data will be anonymized such that only the unique reference numbers will be displayed in the images provided, and participant information including participant enrollment number and surgery information will be removed.
 
9) The types of the images obtained from this procedure are as follows:
 
cCeLL – Ex vivo will capture image data of a resected tissue, prior to frozen sectioning (FS) and permanent sectioning (PS). The biopsied samples can be used to evaluate the presence of tumors, and the tumor types.
 

Method of analysis	Image data	Reference standard	Result of analysis by a pathologist	

cCeLL – Ex vivo	CC	PS	CC-H	

Permanent section	PS	PS		

Frozen Section	FS	PS		

 
CC : Analysis of images obtained by cCeLL FS : Frozen section analysis PS : Permanent section analysis H : Pathologist
 
10) Data will be analyzed by a statistician. Sensitivity and specificity will be calculated as follows:
	Method of analysis	Image data	Reference standard	Result of analysis by a pathologist	cCeLL – Ex vivo	CC	PS	CC-H	Permanent section	PS	PS		Frozen Section	FS	PS	
Method of analysis	Image data	Reference standard	Result of analysis by a pathologist														
cCeLL – Ex vivo	CC	PS	CC-H														
Permanent section	PS	PS															
Frozen Section	FS	PS															

Study Endpoints	

- The probability of interpretation results by the interpreting physician (1 pathologist) being positive given that the reference standards is positive

- The probability of interpretation results by the interpreting physician (1 pathologist) being negative given that the reference standards is negative

 
Primary Endpoint
 
The primary endpoints in this study are the agreement between cCeLL Ex vivo and frozen section, the sensitivity of cCeLL ex vivo and frozen section, and the specificity of cCeLL ex vivo and frozen section. These endpoints will be assessed by a single pathologist in the analysis of tumor tissue.
 
Secondary Endpoints
 

1. Comparison of time taken in tissue scanning, visualization, and interpretation using cCeLL – Ex vivo to time taken in frozen section analysis.

2. Accuracy in determining the tumor type

3. Required image counts for adequate analysis and diagnosis using cCeLL – Ex vivo

4. Non-diagnostic Image

5. AUC value

Analysis Methods	
Primary Endpoints
 
Comparison of the sensitivity/specificity of cCeLL-Ex vivo reading results, and the sensitivity/specificity of the frozen section reading results in one pathological inquiry for brain tumor tissue
 

• Sensitivity of cCeLL-Ex vivo reading result in 1 patient in pathological inquiry for brain tumor tissue: Probability that PS is positive if CC-H positive

• Specificity of cCeLL-Ex vivo reading result in 1 patient in pathological inquiry for brain tumor tissue: Probability that PS is negative if CC-H is negative

• Sensitivity of frozen section reading results for brain tumor tissue: Probability that FS is positive if PS is positive

• Specificity of frozen section reading results from brain tumor tissue: Probability that PS is negative if FS is negative

 
The ratio of the clinical sensitivity/specificity of a cCeLL Ex-vivo image and the sensitivity/specificity of the frozen section image of 1 patient in the pathological inquiry for the total reading results is presented, respectively. To identify a 95 % bilateral confidence interval for the difference between cCeLL- Ex vivo and the frozen section sensitivity/specificity.
 
The statistical significance of the difference between cCeLL-Ex vivo and the frozen section sensitivity/specificity ratio is tested by the McNemar test.
 
Secondary Endpoints
 

1. Comparison of cCeLL-Ex vivo imaging and reading time with frozen section reading time

i. The cCeLL-Ex vivo imaging time is measured and recorded in minutes from the time the fluorescent dye is applied to the specimen for image acquisition

	
ii. The cCeLL-Ex vivo reading time by the pathologist is measured and recorded in minutes from the time of capturing the cCeLL-Ex vivo image of each brain tumor to the time of the final reading.
 
iii. The imaging and reading time for frozen section is measured in minutes from the time of resecting the specimen undergoing frozen section in the operating room to the time when the pathology department of each institution obtains a frozen section image and reports the findings.
 
iv. Format: _____ Hours _____ Minutes
 
2. Comparison of cCeLL accuracy of evaluating the tumor types via Ex-vivo imaging with the accuracy using frozen section
 

i. Evaluation of tumor types via cCeLL-Ex vivo images by 1 pathologist : Agreement between the result of CC-H and the result of PS

ii. Evaluation of tumor types via frozen section: Agreement between the result of FS and the result of PS

 
3. cCeLL – Time and number of images required to diagnose Ex vivo imaging
 

i. The number of images required for the pathologist to read the brain tumor cCeLL – Ex vivo image will be measured and averaged.

ii. cCeLL – Ex vivo reading time uses that of secondary endpoint 1.

iii. *Average number of images required for cCeLL – Ex vivo image reading of 1 brain tumor specimen: _____

 
4. Non-diagnostic image
 

i. The total number of cCeLL Ex-vivo images among the images confirmed in the vivo reading, and the proportion of the number of images that cannot be read are stated as a percentage (%).

ii. The number of images that cannot be read is recorded when the reader reads it.

 
5. AUC value
 

i. Based on the results of each endpoint, the sensitivity and false positive rate (1-specificity) are used to draw the ROC (Receiver Operating Characteristic) Curve to evaluate the performance of the diagnosis to distinguish between positive and negative, and the accuracy of the diagnosis is evaluated through the AUC (Area Under the Curve) value obtained from the area below the ROC curve.

--	--

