### **5.4 Sample Size**

The sample size refers to the number of analyzable tissue samples collected from participants. There may be multiple samples collected from each participant.

There will be 250 analyzable tissue samples required (200 tumor positive and 50 normal) for this study.

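### The Synopsis defines cCeLL sensitivity and both specificities as predictive values, and Section 8.3.1 prints one specificity formula for both methods, so two of the three primary comparisons are wrong if computed as written

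*Combined protocol and SAP*

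**What the plan says.** Sections 8.1 and the Synopsis (Study Endpoints) list three primary endpoints: agreement, sensitivity and specificity of cCeLL and frozen section. Permanent section is the truth: "PS will serve as a reference standard to the analysis result of CC and FS" (Synopsis, Study Procedure).

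The Synopsis Analysis Methods give four definitions:

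- cCeLL sensitivity: "Probability that PS is positive if CC-H positive"
- cCeLL specificity: "Probability that PS is negative if CC-H is negative"
- Frozen-section sensitivity: "Probability that FS is positive if PS is positive"
- Frozen-section specificity: "Probability that PS is negative if FS is negative"

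A 95% two-sided interval for the difference and McNemar's test are to follow.

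The definitions belonging to Study Procedure item 10, also in the Synopsis, run the other way. They give the probability of the reading "being positive given that the reference standards is positive" and of it "being negative given that the reference standards is negative".

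Section 8.3.1 sets up paired tables within truth-positive and truth-negative samples. Its sensitivity numerators are e+f (frozen section) and e+g (cCeLL). The specificity table has cells r, s, t, u, with row margin r+s for frozen section and column margin r+t for cCeLL. Both specificities are nevertheless printed as (r+d)/n2. Non-inferiority is declared if the upper bound of the difference, frozen section minus cCeLL, lies below 5 points (sensitivity) or 10 points (specificity).

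**The concern.** Sensitivity and specificity condition on the truth; predictive values condition on the test result. Three of the four Synopsis definitions condition on the test result. The sensitivity row therefore sets a positive predictive value against a true sensitivity, and the specificity row compares two negative predictive values.

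This matters in three ways:

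- Predictive values depend on the tumor fraction, which the plan fixes at 200/250 = 80% by its collection targets. They are not properties of the device alone.
- A positive predictive value and a sensitivity have different denominators, so the paired McNemar comparison that the Synopsis specifies cannot be formed.
- A positive predictive value hardly responds to missed tumor, which is the error a sensitivity endpoint exists to detect.

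Separately, identical specificity formulas make the point difference zero for any data. The specificity decision then depends only on how many discordant pairs there are, not on which method they favor.

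**Working it through.** **Inputs.** Sample counts: "There will be 250 analyzable tissue samples required (200 tumor positive and 50 normal) for this study" (Section 5.4). Anticipated sensitivity and specificity are 90% for both methods, and the margins are 5 and 10 points (Section 8.3.1). The bound is difference + z × √(discordant pairs)/n. Section 8.3.1 calls it a 97.5% bound (z = 1.96) but prints the multiplier as z with subscript 0.05 (1.645), so both are shown.

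**The plan's own figures.** Section 8.3.1 states that the estimated sensitivity difference stays within 5 points with probability above 90% (n = 200), and the specificity difference within 10 points with probability above 80% (n = 50). The documents give no discordance rate. Assuming independent errors given truth, it is 2 × 0.9 × 0.1 = 0.18.

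- Sensitivity: Φ(0.05/√(0.18/200)) = Φ(1.667) = 0.952
- Specificity: Φ(0.10/√(0.18/50)) = Φ(1.667) = 0.952

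Over discordance 0.20 to 0.10, both run from 0.943 to 0.987. The stated figures reproduce. They use the correct definitions, so they are not affected by this point.

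**Synopsis definitions taken literally.** At 90%/90% the expected counts for either method are 180 true positives, 20 false negatives, 45 true negatives and 5 false positives.

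- cCeLL sensitivity as defined: 180/(180+5) = 180/185 = 97.3%. Frozen-section sensitivity as defined: 180/200 = 90.0%. Two identical methods appear 7.3 points apart, and the denominators are 185 and 200.
- Specificity as defined, either method: 45/(45+20) = 45/65 = 69.2%, against a true 90%.

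Now vary cCeLL alone:

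| True cCeLL sensitivity | True cCeLL specificity | Sensitivity as defined | Specificity as defined |
|---|---|---|---|
| 90% | 90% | 180/185 = 97.3% | 45/65 = 69.2% |
| 85% | 90% | 170/175 = 97.1% | 45/75 = 60.0% |
| 70% | 90% | 140/145 = 96.6% | 45/105 = 42.9% |
| 90% | 80% | 180/190 = 94.7% | 40/60 = 66.7% |

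A 20-point loss of sensitivity moves the quantity labelled sensitivity by 0.7 points. A 5-point loss of sensitivity moves the quantity labelled specificity by 9.2 points, while a real 10-point loss of specificity moves it by only 2.6.

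**Section 8.3.1 specificity formula taken literally.** With both specificities equal to (r+d)/n2, the difference is 0 whatever d means. For k = s + t discordant pairs the bound is z√k/50, to be compared with 0.10.

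- z = 1.96: k = 6 gives 0.096 (pass); k = 7 gives 0.104 (fail)
- z = 1.645: k = 9 gives 0.0987 (pass); k = 10 gives 0.104 (fail)

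If all pairs go against cCeLL, these passes hide observed deficits of 6/50 = 12 points and 9/50 = 18 points. With s = 6 and t = 0, the correct bound at z = 1.96 is 0.12 + 0.096 = 0.216, a clear failure where the printed rule declares non-inferiority.

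**The case against.** The strongest reply is that these are drafting slips which the rest of the plan corrects. The Synopsis sample-size text, the definitions under item 10 and Section 8.3.1 all condition on truth. The confirmatory sensitivity rule in 8.3.1 has the right numerators, so the false 7.3-point advantage could reach a reported estimate or the Synopsis interval, but not the 8.3.1 non-inferiority test. The specificity formula cannot be computed from its own table, so an analyst would notice. The correct margins, r+s and r+t, are printed there, and the text already names s and t as the discordant cells. Where discordance is symmetric, the printed and corrected rules agree. Agreement, the remaining primary endpoint, is untouched, and the plan sets no rule that all three must succeed.

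Much of this stands. The defect is a contradiction rather than a uniformly wrong plan, and the figures above show the effect of literal application, not the expected trial result. Two things remain. The plan holds two incompatible definitions of a primary endpoint, one of which favors the device on sensitivity, and it does not say which governs. For specificity, no correct explicit formula appears anywhere, so the analyst would have to supply one.

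**Conclusion.** The concern holds as stated: computed as written, the primary sensitivity and specificity comparisons are wrong. At the plan's 200/50 mix and 90%/90% assumption, the Synopsis definitions give a spurious 7.3-point sensitivity advantage and a specificity reading of 69.2%. The printed 8.3.1 formula would accept an observed specificity deficit of 12 points (z = 1.96) or 18 points (z = 1.645) against a 10-point margin.

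The predictive values rest on the planned sample counts and anticipated accuracies. The specificity result rests only on n = 50 and the printed bound. Sample size, margins, planning probabilities and the agreement endpoint are not affected. Because this concerns the definition of primary endpoints and a decision formula, it must be corrected before analysis rather than left to interpretation.

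**What to change.** - **Synopsis, Analysis Methods:** define sensitivity as P(CC-H+ given PS+) and P(FS+ given PS+), and specificity as P(CC-H− given PS−) and P(FS− given PS−).
- **Section 8.3.1:** set p_SpeF = (r+s)/n2 and p_SpeC = (r+t)/n2, keeping s and t as the discordant cells. In the closing paragraph, label the specificities p_SpeF and p_SpeC; they now carry the sensitivity labels.
- **In the same edit, tidy the related notation in 8.3.1:** write the sensitivity denominator as n1, as in the Synopsis. It is printed as n_T, which is also the agreement total; read as 250, it would turn 90% into 180/250 = 72%. Make the discordant-cell letters in the standard error (b and c) match the text (a and b), and correct the SpeCF subscript in the specificity null hypothesis.

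The cost is a wording amendment to two places, with no new data and no change to sample size or margins.

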**Agreement Table**

		cC		
FS Results	Agree	DisAgree		
	a	b	a+b	
Disagree	c	d	c+d	
		a+c	b+d	n T

The estimate of agreement is  $p_{AG} = (a+d)/n_T$ . It is desired to test the hypothesis that the agreement is greater than 80%. This is compatible with the expected result that both the sensitivity and the specificity will be about 90%. Thus the hypothesis to be tested is that the agreement is 80% (H0: Null hypothesis) versus the alternative hypothesis that the agreement is greater than 80% (HA: Alternative hypothesis).

$$H_0: \pi_{AG} = 80\% \text{ vs } H_A: \pi_{AG} > 80\%$$

Where  $\pi_{AG}$  is the percent agreement between Frozen Section and cCell. This will be tested utilizing the exact binomial test. Estimates of agreement from the pilot study indicate that the agreement will be greater than 86%. In this study, there will be 250 participants available for analysis for the estimation and testing of agreement. For outcome results, if the agreement is 86%, with the sample size of 250, the probability the estimated agreement will be greater than 80% is greater than 90%. That is,  $P(p_{AG} > 80\%) > 90\%$ .

**Sensitivity Table** – Sensitivity is only calculated when the truth standard is positive for tumor.

Agreement Table with Tumor Truth

		cC		
FS Results	Agree w/Truth	Disagree w/Truth		
	e	f	e+f	
Disagree	g	h	g+h	
		e+g	f+h	n T

The sensitivity of the Frozen Section is given by  $p_{SenF} = (e+f)/n_T$  and the sensitivity of cCell is given by  $p_{SenC} = (e+g)/n_T$ . It is desired to demonstrate that the sensitivity of cCell is non inferior to that of Frozen section.

The non inferiority of the sensitivity of cCell result versus the sensitivity of the Frozen Section is given as:

$$H_0: \pi_{SenF} - \pi_{SenC} > \Delta \text{ versus } H_A: \pi_{SenF} - \pi_{SenC} \leq \Delta$$

Here  $\pi_{SenF}$  is the true sensitivity for Frozen Section and  $\pi_{SenC}$  is the true sensitivity for cCell. The parameter  $\Delta$  is the non-inferiority limit. In this study, it is proposed to utilize a  $\Delta=0.05$  (5%). If that  $\Delta$  is used and the anticipated sensitivity for both Frozen Section and cCell is 90%, then

with a sample size of 200 tumor positive samples the probability the difference between the estimated sensitivities is less than 5% is greater than 90%. That is  $P((\pi_{\text{SenF}} - \pi_{\text{SenC}} \leq 5\%) > 90\%.$

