**Specificity Table** – Specificity is only calculated when the truth standard is negative for tumor.

Agreement Table with Non-Tumor Truth

		cC		
FS Results	Agree w/Truth	Disagree w/Truth		
Agree	r	s	r+s	
Disagree	t	u	t+u	
		r+t	s+u	$n_2$

The specificity of the Frozen Section is given by  $p_{\text{SpeF}} = (r+d)/n_2$  and the specificity of cCeLL is given by  $p_{\text{SpeC}} = (r+d)/n_2$ . It is desired to demonstrate that the specificity of cCeLL is non-inferior to that of Frozen section.

The non-inferiority of the specificity of cCell result versus the specificity of the Frozen Section is given as:

$$H_0: \pi_{\text{SpeCF}} - \pi_{\text{SpeC}} > \Delta \text{ versus } H_A: \pi_{\text{SpeF}} - \pi_{\text{SpeC}} \leq \Delta$$

Here  $\pi_{\text{SpeF}}$  is the true specificity for Frozen Section and  $\pi_{\text{SpeC}}$  is the true specificity for cCell. The parameter  $\Delta$  is the non-inferiority limit. In this study, it is proposed to utilize a  $\Delta=0.10$  (10%). If that  $\Delta$  is used and the anticipated specificity for both Frozen Section and cCell is 90%, then with a sample size of 50 tumor negative samples the probability the difference between the estimated specificities is less than 10% is greater than 80%. That is  $P(\pi_{\text{SpeF}} - \pi_{\text{SpeC}} \leq 10\%) > 80\%.$

The sensitivity and the specificity hypotheses will be tested using McNemar's test by constructing an upper 97.5% confidence bound for the difference between the two methods. If the upper bound is less than  $\Delta$  (5% for sensitivity and 10% for specificity) then the two images are said to be non-inferior. The upper confidence bound is given by:

$$p_{\text{FS}} - p_{\text{cC}} + z_{0.05} \text{se}(p_{\text{FS}} - p_{\text{cC}}), \text{ where}$$

$$\text{se}(p_{\text{FS}} - p_{\text{cC}}) = \frac{\sqrt{(b+c)}}{n}$$

The standard error (se) for the difference depends on the number of discordant pairs (a and b). Where a and b correspond to f and g from the sensitivity table and to t and s from the specificity table. The estimates  $p_{\text{FS}}$  and  $p_{\text{cC}}$  correspond to the sensitivity of the Frozen Section,

$p_{\text{SenF}}$ , and the sensitivity of cCell,  $p_{\text{SenC}}$  when sensitivity is being tested and they correspond to the specificity of the Frozen Section,  $p_{\text{SenF}}$ , and the specificity of cCell,  $p_{\text{SenC}}$ , when specificity is being tested.

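### The Synopsis tests sensitivity and specificity for a difference with McNemar's test, while the plan's aim and the rule in section 8.3.1 are non-inferiority; the two must be reconciled

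*Combined protocol and SAP*

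**What the plan says.** **Synopsis, Analysis Methods, Primary Endpoints.** The only test named for sensitivity and specificity is this: "The statistical significance of the difference between cCeLL-Ex vivo and the frozen section sensitivity/specificity ratio is tested by the McNemar test". The sentence before it asks: "To identify a 95 % bilateral confidence interval for the difference between cCeLL- Ex vivo and the frozen section sensitivity/specificity". Neither sentence carries a margin, a direction or a success rule.

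**Synopsis, Basis for Calculating the Number of Acquired Images.** For sensitivity the aim is different: "It is desired to demonstrate that the sensitivity of cCeLL is non inferior to that of Frozen section". The margin is 5%. The Synopsis has no corresponding hypothesis, margin or rule for specificity.

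**Section 8.3.1.** Non-inferiority hypotheses are given for both endpoints. They are to be tested with McNemar's test, "by constructing an upper 97.5% confidence bound for the difference between the two methods". The rule compares the upper bound with the margin: "5% for sensitivity and 10% for specificity) then the two images are said to be non-inferior". The formula for the bound carries the multiplier z with subscript 0.05, although the text says 97.5%.

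Nothing says which section governs.

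**The concern.** McNemar's test has the null hypothesis that the two methods have equal sensitivity (or specificity). Failing to reject it does not show that cCeLL is within 5 or 10 points of frozen section. Rejecting it does not show that cCeLL is outside those margins. An analyst who follows the Synopsis therefore tests a different hypothesis from one who follows 8.3.1.

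Section 8.3.1 blurs the distinction by giving its bound the name of the equality test. A reader could take the two sections as one analysis. If the conflict stays, the choice between them could be made after the results are known. Section 8.3.1 also says that no power calculations were done, so no stated power would help in interpreting a non-significant difference.

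**Working it through.** **Inputs from the documents.** 200 tumor-positive and 50 normal analyzable samples (5.4). Anticipated sensitivity and specificity of 90% for both methods, and margins of 5% and 10% (8.3.1). Expected agreement above 86% (8.3.1). Standard error = √(discordant pairs)/n (8.3.1).

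**Input that must be assumed.** The documents give no discordance between the two methods within tumor or within normal samples. I use up to 20%. Two reference values are 14% (1 − 0.86, the overall agreement figure) and 18% (independent readings at 90%/90%: 2 × 0.9 × 0.1). The smallest discordance compatible with a deficit equal to the margin is 5% for sensitivity and 10% for specificity.

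**Step 1: the plan's own figures.** With both methods at 90% and 18% discordance:
- Sensitivity, P(estimated difference ≤ 5%): normal approximation Φ(0.05/√(0.18/200)) = Φ(1.67) = 0.952; exact 0.960. The plan says above 90%.
- Specificity, P(estimated difference ≤ 10%): Φ(0.10/√(0.18/50)) = Φ(1.67) = 0.952; exact 0.967. The plan says above 80%.
- Agreement, P(estimate > 80%) at a true 86%, n = 250: 0.994. The plan says above 90%.

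These reproduce as lower limits. They are not powers for either test.

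**Step 2: same data, two analyses.** Let f be the pairs where only frozen section is right and g those where only cCeLL is right. McNemar: z = (f − g)/√(f + g). Bound: (f − g)/n + 1.96 √(f + g)/n.

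| f, g, n | Deficit | McNemar z | p, asymptotic (exact) | Upper 97.5% bound | Margin |
|---|---|---|---|---|---|
| 20, 10, 200 | 5% | 10/√30 = 1.83 | 0.068 (0.099) | 5% + 1.96 × 2.74% = 10.4% | 5%, not met |
| 8, 3, 50 | 10% | 5/√11 = 1.51 | 0.13 (0.23) | 10% + 1.96 × 6.63% = 23% | 10%, not met |
| 5, 0, 200 | 2.5% | 5/√5 = 2.24 | 0.025 (0.0625) | 2.5% + 1.96 × 1.12% = 4.7% | 5%, met |

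The first two rows show no significant difference, yet non-inferiority fails. The third is significantly worse by the asymptotic test, yet non-inferior. This second kind of disagreement is narrow. It arises only for sensitivity, only at 4 versus 0 or 5 versus 0, and not with the exact test.

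**Step 3: illustration at a true deficit equal to the margin.** I enumerated the discordant pairs exactly: f + g binomial, and f given f + g binomial, with the two discordant probabilities differing by the margin. The entries are the probability that McNemar is non-significant at two-sided 5%, and the probability that the 8.3.1 bound with 1.96 passes.

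| Endpoint | Assumed discordance | McNemar non-significant, asymptotic (exact) | Bound passes |
|---|---|---|---|
| Sensitivity, n = 200, deficit 5% | 5% | 1% (6%) | 6% |
| | 10% | 36% (46%) | 3% |
| | 14% | 51% (60%) | 3% |
| | 20% | 65% (70%) | 3% |
| Specificity, n = 50, deficit 10% | 10% | 25% (62%) | 11% |
| | 14% | 51% (68%) | 6% |
| | 20% | 67% (76%) | 4% |

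**Step 4: the printed multiplier.** With 1.645 in place of 1.96, the bound passes at the margin in 6.1% (10% discordance) to 5.3% (20%) of trials for sensitivity. For specificity the figures are 11.2% to 6.5%. So the 8.3.1 rule cannot be copied into the Synopsis until 97.5% and z with subscript 0.05 are reconciled.

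**The case against.** The strongest reply is that the only decision rule for these endpoints is the correct one. Section 8.3.1 compares a bound with a margin. The Synopsis interval, taken as frozen section minus cCeLL, has an upper limit at the same level as a one-sided 97.5% bound. Section 8.3.1 also uses McNemar's name for that bound, so the Synopsis sentence may be only a loose summary of it.

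Much of this stands. A reader might infer that the plan lets a non-significant McNemar result count as success, and so that the percentages in Step 3 are false-success rates. The documents do not support that: no section states such a rule. A reader might also infer that non-significance would be the usual outcome at the margin. That depends on assumed discordance. For sensitivity it is about 1% at the minimum discordance of 5%. For specificity the asymptotic figure starts at 25% and reaches one half only at about 14%. The Synopsis does not say whether the test is exact or asymptotic.

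The reply does not remove the conflict. The Synopsis sentence speaks of the statistical significance of a difference in a ratio, which is not a bound against a margin. Its interval is not linked to any margin, and specificity non-inferiority is missing from the Synopsis altogether.

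**Conclusion.** The concern holds as an inconsistency in the primary analysis of sensitivity and specificity. The Synopsis specifies a test of equality and an unanchored interval, where the stated aim and 8.3.1 require non-inferiority. It should be corrected before analysis.

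The examples in Step 2 need no assumption about discordance; they show that the choice of section can change the conclusion. The probabilities in Step 3 illustrate the risk if a non-significant result were misread. They rest on assumed discordance and on a true deficit exactly at the margin, and they do not describe a rule in the plan. Agreement has its own exact binomial test against 80% and is not touched.

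**What to change.** - **Synopsis, Analysis Methods:** replace the McNemar sentence with the 8.3.1 rule for both endpoints. cCeLL is non-inferior if the upper limit of the two-sided 95% interval (equivalently the one-sided 97.5% bound) for frozen section minus cCeLL is below 5% for sensitivity and below 10% for specificity.
- **Section 8.3.1:** describe the procedure as a confidence bound for a paired difference, not as McNemar's test. Replace z with subscript 0.05 by z with subscript 0.025 (1.96), so that it matches the stated 97.5%.
- **Any McNemar p-value that is kept:** label it descriptive, with no bearing on the non-inferiority conclusion, and say whether it is exact or asymptotic.

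The cost is an amendment to the wording of the Synopsis and 8.3.1. Sample size and data collection do not change.
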